3.0 Introduction

This Statistical Analysis Plan (SAP) describes the statistical methods that will be used during the analysis and reporting of data collected under Amolyt Pharma Protocol AZP-3601-CLI-001. This SAP covers and the analyses to

be performed for Part C (study conducted in patients with hypoparathyroidism).

This SAP should be read in conjunction with the study protocol. This version of the SAP has been developed using the global protocol version 5.0 dated 12-May-2021, and the country specific protocol amendments dated 17-Mar-2021 for Netherlands, 8-Apr-2022 for France (Version 7.0) and 11-Apr-2022 for Hungary and Spain (Version 7.0) (including all amendments up to this protocol date).

An approved and signed SAP is a requirement for database lock. An approved SAP is also required for unblinding of the study treatments.

This SAP only covers the results that will be processed by the PRA Early Development Services (EDS) Biostatistics Department.

PRA EDS will perform the pharmacokinetic (PK), pharmacodynamic (PD), and safety and tolerability evaluation.

This SAP supersedes the statistical considerations identified in the protocol; where considerations are substantially different, they will be identified. Any post-hoc or unplanned analyses, or significant changes from the planned analysis in this SAP performed to provide results for inclusion in the clinical study report (CSR) but not included in this SAP, will be clearly identified in the CSR. Changes to planned analyses do not require an updated SAP but should be included in the CSR if significant.

4.0 Changes from Previous Version of Approved SAP

Version 2.0:

- Overall changes based on updated versions of the protocol.
- Inclusion of the analyses related to Part C (Main treatment period and Extension phase)

Version 3.0:

- Inclusion of additional PK samplings of AZP-3601 in plasma at D84, during the Extension phase of part C according to protocol version 7.0
- Added listing of SF-36 Questionnaire Physical and Mental Component Score (Part C only)

5.0 Study Objectives

5.1 Primary

•

- To assess the safety and tolerability of AZP-3601 following single and 4-week multiple ascending doses administered by sc injection to patients with hypoparathyroidism (HP) (Part C, Main Treatment Period)
- To assess the safety and tolerability of AZP-3601 during a 2-month treatment extension period (Part C, Extension Phase) in patients with HP

EDSREP 009 T 01 G Page 4 of 53

Protocol: AZP-3601-CLI-001 Version Date: 26-Aug-2022

5.2 Secondary

•

- To assess the PD response of AZP-3601 on maintenance of serum calcium and phosphate levels within a target range while oral calcium and active vitamin D are progressively reduced, following multiple ascending doses administered by sc injection to patients with HP (Part C, Main Treatment Period)
- To assess the PK of AZP-3601 following single and multiple ascending doses administered by sc injection to patients with HP (Part C)
- To assess the feasibility of individual titration of AZP3601 during a 2-month treatment extension period (Part C, Extension Phase) in patients with HP (ie if individual dosing across a dose range can be implemented in a safe and effective manner and can be maintained throughout the treatment period)

5.3 Exploratory

•

- To assess the effect of AZP-3601 on urinary excretion of calcium and phosphate as well as on bone turnover biomarkers following multiple ascending doses administered by sc injection to patients with HP (Part C, Main Treatment period)
- To assess the effect of AZP-3601 on urinary excretion of calcium and phosphate as well as on bone biomarker and Bone Mineral Density (BMD) as assessed by Dual-Energy X-Ray absorptiometry (DXA) during a 2-month treatment extension period (Part C, Extension Phase)

6.0 Study Design

[figure not shown]
This is a first-in-human (FIH) study in healthy subjects followed by a study in patients with HP combined in a single protocol.

Part B will be

followed by a MAD part in patients with HP who will receive AZP3601 for 4 weeks (Part C).

Patient completing the 4 weeks Main Treatment Period of Part C, will be offered to enter a 2-month open label treatment extension phase. Together with the initial 4-weeks treatment period, this extension phase will allow the collection of safety and PD data over a total of 3 months of treatment.

In all study parts, safety, tolerability, PK (Part C), and PD of sc doses of AZP - 3601 will be assessed.

EDSREP 009 T 01 G Page 5 of 53

Statistical Analysis Plan AZP20005-20005X

Protocol: AZP-3601-CLI-001 Version Date: 26-Aug-2022

	I	

EDSREP 009 T 01 G Page 6 of 53

Protocol: AZP-3601-CLI-001 Version Date: 26-Aug-2022

[figure not shown]

Part C (MAD part in patients with HP)

Part C will be an open-label MAD study in male or female patients with HP who are on treatment with oral calcium and active vitamin D to evaluate the safety and tolerability, PK, and PD of AZP-3601. Up to 2 cohorts of approximately 12 patients each are planned for this part of the study.

Part C, Main Treatment Period

The figure below illustrates the study design for Part C for the Main Treatment Period.

Prior to the treatment period, there will be an optimization period of up to 8 weeks during which doses of oral calcium and active vitamin D will be adjusted to achieve a baseline target range of albumin-corrected serum calcium (7.8 to 9.0 mg/dL) and therefore ensuring a common baseline for all patients.

During this optimization period, any serum 25hydroxy vitamin D (native vitamin D) and/or magnesium deficiencies will be corrected.

EDSREP 009 T 01 G Page 7 of 53

Version Date: 26-Aug-2022

During the main treatment period, patients in Part C will receive AZP-3601 for 28 days as daily sc abdominal injections (with rotation of injection sites every dosing day). Doses of oral calcium and active vitamin D supplements will be carefully reduced during the initial 14 days of treatment while maintaining albumin-corrected serum calcium in the target range (7.8 to 9.0 mg/dL). Reductions of both oral calcium and active vitamin D supplements will be performed using a staged approach until the active vitamin D dose can be eliminated and the oral calcium dose can be reduced to or below 500 mg/day (please note that throughout this protocol doses of oral calcium refer to doses of elemental calcium). Based on animal data, serum calcium is expected to increase progressively following repeated administration of AZP-3601 and PD steady state is expected to be observed within the first 5 days of dosing. Staggered reductions of doses of oral calcium and active vitamin D supplements will therefore be performed at near-steady state based on the predose albumin-corrected serum calcium value. It is anticipated to perform reduction of supplements on Day 5, 8, and 11. The days of dose reduction of supplements may change based on data from Part B; they may be advanced or delayed based on (but not limited to) when the PD steady state is observed.

If independence from active vitamin D and reduction of oral calcium is not achieved on Day 14 (ie, elimination of active vitamine D and reduction of oral calcium to or below 500 mg/day), the AZP-3601 dose will be increased and patients will be treated at this dose for the remaining duration of the treatment period (up to Day 28). Patients achieving independence from active vitamin D and reduction of oral calcium on Day 14 will remain at the same dose level. The last remaining daily dose of oral calcium, if any, may be removed on Day 17 based on the predose albumin-corrected value of serum calcium.

Patients will undergo frequent testing for albumin-corrected serum calcium and phosphate during the initial 14-day treatment period and again following increase of the dose. In addition, there may be additional and unscheduled checks for albumin-corrected serum calcium and phosphate at the discretion of the Investigator.

At any time during the study, hypercalcemia and hypocalcemia will be managed by adjustment in active vitamin D and/or oral calcium supplementation. Adjustments will be based on laboratory values including albumin-corrected serum calcium and serum phosphate as well as on symptoms and will be performed at the Investigator's judgment. As a general guidance, adjustments should be performed when calcium values are outside the target range of 7.8 to 9.0 mg/dL.

The following treatments are planned to be administered in Part C in an open-label fashion:

Cohort C1: sc doses of 20 µg AZP-3601 (n=12) qd from Day 1 to Day 28 (dose of AZP-3601 may be increased to 40 µg from Day 14 onwards)

Cohort C2: sc doses of a fixed dose up to 40^a µg AZP-3601 (n=12) qd from Day 1 to Day 28 (dose of AZP-3601 may be increased at a fixed dose up to 60 µg from Day 14 onwards)

During the extension phase, patients may have their AZP-3601 dose increased in increments of $10^a \mu g$ to a maximum dose of $60^a \mu g$ (Cohort 1) and of $80^a \mu g$ (Cohort 2).

The planned dose levels (including the dose levels allowed to increase the dose in the same cohort) may be changed following review of data from Parts A and B, and the emerging data from Part C. However, for each of the cohorts the doses will not exceed the doses previously tested in Part A and

EDSREP 009 T 01 G Page 8 of 53

Version Date: 26-Aug-2022

Part B. In addition, the increase from one dose level to the next dose level within the same cohort or between cohorts will not be more than 3-fold.

Part C may commence after the first 3 cohorts of Part B have been completed, providing there is sufficient appropriate data available (safety and tolerability, PK, and PD) to enable determination of dose levels.

The following table provides an overview of the doses (µg) planned to be adminstered in Part C

					1
D 1001 1				0.45	Ooh
Part C Cohort				C1 ^b	C2 ^b
				20 (dose 1)	fixed dose
				40 (dose 2)	up to 40
					(dose 1)
					fixed dose
					up to 60
					(dose 2)

^a Part B may commence following completion of the first 3 cohorts of Part A.

Although this is an ascending dose study, a lower dose may be administered in the second cohort based on the safety, tolerability, or available PD and plasma PK results of the first cohort. Also, the same dose may be tested or an intermediate dose may be tested to gain more information on safety, tolerability, PD, and/or PK.

There will be an interval of at least 7 days between the last dose in the first cohort and the first dose in the second cohort. Patients included in the first cohort cannot participate in the second cohort.

[figure not shown]
Part C, Extension Phase

The figure below illustrates the study design for Part C for the Extension Phase.

EDSREP 009 T 01 G Page 9 of 53

^b Part C may commence after completion of the first 3 cohorts of Part B.

Protocol: AZP-3601-CLI-001 Version Date: 26-Aug-2022

Patients completing the 4 weeks Main Treatment Period of Part C, will be offered to enter a 2-month open label treatment extension phase. For patients willing to enter the extension phase, an informed consent form (ICF) should be signed on Day 28 at the latest.

Patients will have to complete study assessments up to Day 28, as described in Schedule of Assessments Table 4 (in the Appendix 2) and from Day 29 onwards, as described in Table 5 (in the Appendix 2).

Patients who will not participate to the Extension phase will have to complete study assessments as described in Table 4 (in the Appendix 2).

The 2-month open label treatment extension phase will start immediately following Day 28 visit of the Main treatment period. Patients will receive AZP-3601 for 56 days (2 months) as daily sc injections from Day 29 onwards (with rotation of injection sites each day of administration).

The goal is to optimize AZP-3601 dosing across a dose range while doses of oral calcium and active vitamin D are as low as safely possible and albumin-corrected serum calcium is maintained within the target range of 7.8 to 9.0 mg/dL (1.95 to 2.25 mmol/L) together with an optimal control of the symptoms of hypoparathyroidism.

For patients who are taking minimal or no supplemental calcium (≤500 mg/day) and no vitamin D on Day 28, the AZP-3601 dose from the previous 14 days of treatment (Part C, Main Treatment Period) can be maintained and adjusted when needed during the Extension Phase.

For patients who are still taking active vitamin D and/or more than 500 mg/day of oral calcium on Day 28, a progressive reduction of supplements will be carried out while increasing the dose of AZP-3601.

On Day 29 onwards, patients will continue on the same dose of AZP-3601 as on Day 28, then individual titration of AZP-3601 may start as early as Day 30 and patients may have their dose of AZP-3601 adjusted at any time during the Extension Phase. Patients may have their AZP-3601 dose increased, as

EDSREP 009 T 01 G Page 10 of 53

Version Date: 26-Aug-2022

defined in previous section, with the goal of achieving or maintaining albumin-corrected serum calcium in the target range of 7.8 to 9.0 mg/dL.

The AZP-3601 dose may be adjusted downward at any time as needed to maintain albumin-corrected serum calcium within the target range or for any safety concerns.

Once patients achieve a stable albumin-corrected serum calcium with the minimum doses of supplements, they will be maintained at that dose of AZP-3601. A separate titration guideline to help the investigator and to facilitate a standardized approach to dose adjustment, will be provided to the clinical site.

Patients will have their serum calcium/Albumin levels measured within 5 days after any adjustment of AZP-3601 and any other time at the discretion of the investigator. The investigator will be free to perform any other serum or urine test if needed.

In addition, there may be additional and unscheduled checks for serum calcium and phosphate at the discretion of the investigator.

At any time during the study, hypercalcemia and hypocalcemia will be managed by adjustment in active vitamin D and/or oral calcium supplementation. Adjustments will be based on laboratory values including albumin-corrected serum calcium and serum phosphate as well as on symptoms and will be performed at the Investigator's judgment.

6.1 Sample Size Considerations

[figure not shown]
This is an exploratory trial for which no formal statistical hypothesis testing will be performed and therefore no formal sample size calculations have been done. The sample size is based on the desire to obtain adequate safety, tolerability, PK and PD data and is considered sufficient to achieve the objectives of the study while exposing as few subjects as possible to the investigational product and study procedures. This sample is typical for a FIH study. Any p-values to be calculated according to the SAP will be interpreted in the perspective of the exploratory character of this study.

6.2 Randomization

EDSREP 009 T 01 G Page 11 of 53

Version Date: 26-Aug-2022

Part C is not randomized. All patients will receive AZP-3601 and no placebo will be administered. patients will be assigned to a cohort based on their availability. After obtaining written informed consent, patients will be screened according to the inclusion and exclusion criteria. Patients will be assigned unique patient numbers allocated in ascending order within the clinical site, that identify the study site and the individual subject. The patient number will be as follows: XXX-YYY, with XXX for country and site number, and YYY for patient counter. Any replacement patient will receive the number of the patient to be replaced, increased by 500 (thus XXX-501 as replacement for XXX-001).

7.0 Overview of Planned Analysis

[figure not shown]
7.1 Changes from Protocol

The PK parameter AUC₀₋₆ will be provided whereas AUC₀₋₁₂ and AUC₀₋₂₄ will not be provided, because the drug is expected to eliminate quickly and because of the scheduled timepoints of PK assessments.

The PK parameter AUC_{0-inf} will be calculated at Day 1 for Control C, therefore kel will be also calculated at this timepoint as well as Adj R².

An additional analysis set (Enrolled Set) will be derived for Part C. The adverse events (AEs) in Part C will also be summarized for Enrolled Set.

7.2 Interim Analysis

For Par C, following completion of Cohort C1, an interim PK/PD report will be provided in a descriptive way, along with a dose escalation report (DER) describing the safety and tolerability, and available pharmacodynamic and pharmacokinetic data, to assist the SRC in dose escalation decision from Cohort C1 to Cohort C2.

EDSREP 009 T 01 G Page 12 of 53

Version Date: 26-Aug-2022

The following PK/PD data will be included in the interim reports:

- PK: AZP-3601 plasma (pg/mL)
- PD: Serum Calcium (mg/dL)
- Serum Calcium corrected for Albumin (mg/dL)
- Serum Inorganic Phosphorus (mg/dL)
- Serum PTH, Intact (pg/mL)
- Urine Calcium excretion rate (estimated, mg/24h)
- Urinary fractional excretion of calcium (%)
- Urinary fractional excretion of inorganic phosphorus (%)
- ADAs

The interim safety reports will be generated by Principal Investigator (data is extracted from the system Oracle EDC).

7.3 Final Analysis

Draft TFLs will be provided

after the database lock of Part C.

After Sponsor comments have been incorporated, the TFLs will be finalized and incorporated in the final CSR.

8.0 Definitions and General Analysis Methods

8.1 Analysis Data Presentation

8.1.1 Rounding

In listings, data will be presented with the same precision as the original data. Derived data will be rounded for presentation purposes.

For all summaries, except PK data summaries, the mean and median will be presented to one decimal place greater than the listed data, standard deviation (SD) to two greater than the listed data, and the minimum and maximum will be presented to the same number of decimal places as the listed data. Frequency percentages will be presented with one decimal.

For all PK data (i.e. concentrations and derived parameters) summaries, descriptive statistics will be presented as integers when values are ≥100 or presented with 3 significant figures when values are <100. The t_{max} values and descriptive statistics thereof will be reported with 2 decimals. Ratios will be presented with 1 decimal. The coefficient of variation (CV%) will be reported with 1 decimal.

P-values will be reported to four decimal places; p-value less than 0.0001 will be reported as p <0.0001.

8.1.2 Imputation

Unless otherwise noted, data will not be imputed. Exceptions are missing start and end times of adverse events (AEs), see Section 17.1.1, PK concentrations below lower limit of quantification (LLOQ), see Section 15.2, PTH(1-84) concentrations below LLOQ, see Section 16.2.2.1, and missing score in SF-36 Questionnaire, see section 16.1.5.

8.1.3 Descriptive Statistics

Unless otherwise indicated, continuous variables will be summarized with the following descriptive statistics: number of observations (n), (arithmetic) mean, SD, minimum (min) value, median, and maximum (max) value. For PK data, geometric mean and geometric CV will be presented in addition.

• Geometric mean = exp(m), where m is the arithmetic mean of the log-transformed data.

EDSREP 009 T 01 G Page 13 of 53

Version Date: 26-Aug-2022

Geometric CV (%): sqrt(exp(s*s)-1)*100, where s*s is the variance of the log-transformed data.

Categorical data will be summarized with frequencies and percentages. Percentages by categories will be based on the number of subjects exposed within a treatment.

For categorical data, the categories will be presented in the tables exactly as they appear in the electronic case report form (eCRF) / Database. No data manipulation will be done for presentation purposes.

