9.1 Safety Set

All subjects who have received at least 1 dose of AZP-3601 or placebo.

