9.4 Enrolled Set (Part C only)

All patients who sign the informed consent form.

The table of "Disposition Summaries" will be presented from "All Subjects", including summarizing the members of each analysis set. Moreover, all the listings will also be presented from "All Subjects".

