12.0 Demographic and Baseline Characteristics

12.1 Demographics

All demographic data will be listed by subject.

Subject demographics will be summarized descriptively for all subjects by study part and ______/cohort (for Part C) as well as overall within each part. The summary will include the subjects' age (in years), gender, race (if available), ethnicity, weight (in kg), height (in cm), and body mass index (BMI) (in kg/m²) at baseline. In addition, for Part C, the number and percentage of subjects will be summarized by age group '<45 years', '≥ 45 and <65 years' and '≥65 years'. Demographics will be summarized for the safety, PK, PD and enrolled sets if applicable.

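### SAP 8.1.3 bases every categorical percentage on dosed subjects, which gives wrong Enrolled Set percentages for demographics and for the all-AE row once any consented patient is never dosed

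*SAP*

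**What the plan says.** SAP 8.1.3 (Descriptive Statistics) states: "Categorical data will be summarized with frequencies and percentages". It then fixes the denominator: "Percentages by categories will be based on the number of subjects exposed within a treatment". The sentence on continuous variables in the same section allows for exceptions; the sentence on percentages does not.

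Two analysis sets matter here:

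- Safety Set (SAP 9.1): "All subjects who have received at least 1 dose of AZP-3601 or placebo".
- Enrolled Set (SAP 9.4, Part C only): "All patients who sign the informed consent form". Dosing is not required.

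Summaries are planned on the Enrolled Set. SAP 7.1 says: "The adverse events (AEs) in Part C will also be summarized for Enrolled Set". SAP 12.1 says: "Demographics will be summarized for the safety, PK, PD and enrolled sets if applicable", and for Part C it adds that "the number and percentage of subjects will be summarized by age group". The table in SAP 9.0 ticks disposition, demographics and AE summaries for this set.

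Consent comes before eligibility is known (SAP 6.2): "After obtaining written informed consent, patients will be screened according to the inclusion and exclusion criteria". The protocol then allows up to 8 weeks of supplement optimization before the first dose. Its Table 3 marks AE monitoring from Week -8 and checks eligibility again on Day -1.

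**The concern.** In an Enrolled Set table the numerator can include patients who consented and were never dosed, while the written denominator leaves them out. A percentage whose numerator is not contained in its denominator is not a proportion, and nothing keeps it at or below 100%.

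Never-dosed patients are a realistic group. Patients can fail screening, or leave or become ineligible during the optimization weeks, after signing consent. If every consented patient were dosed, the Enrolled Set would equal the Safety Set and a second AE summary would add nothing.

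What is at stake is the credibility of some Part C tables: sex or age-group percentages that do not total 100%, and an all-AE percentage that overstates how many consented patients had an event.

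**Working it through.** The SAP makes no formal sample size calculation and states no figure that this point disputes. The only planned count is 2 cohorts × about 12 = about 24 dosed patients, which agrees with the protocol's approximate total of 24.

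**Inputs**
- Dosed patients, E = 24 (protocol and SAP, Part C design).
- Never-dosed share of enrolled patients, f: not in the documents. Assumed 10% to 30%.
- Enrolled patients, N = E / (1 − f).

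**Demographics.** The categories of one variable are mutually exclusive and together contain all N enrolled patients. Under 8.1.3 as written they total 100 × N / E = 100 / (1 − f) percent.

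| f (assumed) | N = 24/(1 − f) | Total as written | N rounded up | Total with rounded N |
|---|---|---|---|---|
| 10% | 26.7 | 111% | 27 | 27/24 = 112.5% |
| 20% | 30 | 125% | 30 | 30/24 = 125.0% |
| 30% | 34.3 | 143% | 35 | 35/24 = 145.8% |

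The direction does not depend on f. One never-dosed patient already gives 25/24 = 104.2%. With none, the total is 100%. With N as the denominator it is always 100%.

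A single category passes 100% when its share of enrolled patients exceeds E/N: 24/27 = 88.9% at f = 10%, 24/30 = 80.0% at 20%, 24/35 = 68.6% at 30%. For example, at 30% a category holding 26 of 35 enrolled patients would print 26/24 = 108.3% instead of 26/35 = 74.3%.

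**All-AE row.** The overall AE table in SAP 17.1.1 has a row for all AEs as well as treatment-emergent rows. Take 24 dosed and 6 never dosed (assumed):
- 22 dosed and 3 never-dosed patients with an AE: 25/24 = 104.2% as written, against 25/30 = 83.3%.
- 20 dosed and 3 never-dosed patients with an AE: 23/24 = 95.8% as written, against 23/30 = 76.7%. The figure is too high even when it looks plausible.

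**Treatment-emergent rows.** SAP 17.1.1 ties these events to dosing, so never-dosed patients should not enter the numerator. With 22 of 24 dosed patients affected, the rule gives 22/24 = 91.7%, the same as in the Safety Set. Dividing by the enrolled number instead gives 22/30 = 73.3%, which dilutes the rate with patients who were never at risk. Here the dosed denominator is the right one. One small leak exists: SAP 17.1.1 assumes that an AE with a missing start date began after treatment, so such an AE in a never-dosed patient might be counted as treatment-emergent.

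**The case against.** The strongest reply is that the table shells (SAP Appendix 4) would normally settle column totals and denominators, and they are not in the supplied text. The error is also easy to see in draft tables, which the sponsor reviews before they are final (SAP 7.3), and the set-specific demographics carry an if-applicable qualifier. This limits the practical risk but does not remove the conflict: shells that use the enrolled number would contradict 8.1.3. Where the SAP wants another denominator it can say so, as it does for menopause status in 12.2. It does not do so for the Enrolled Set.

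Four stronger readings are tempting, and the documents do not support them:

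- *Every Enrolled Set AE percentage is inflated.* The treatment-emergent rows are not, as shown above. SAP 17.1.1 also specifies numbers of subjects and events for these AE tables, so AE percentages arise only through the general rule in 8.1.3.
- *Never-dosed patients have no column.* Part C demographics (12.1) and the AE tables (17.1.1) include an overall column, and SAP 6.2 assigns patients to cohorts by availability. What is missing is a statement of where they are counted.
- *Disposition is affected in the same way.* SAP 9.4 says that this table is presented from all subjects, so its base is named.
- *The Enrolled Set AE table exists to capture run-in events.* That is a plausible use, but the SAP gives no reason for the table.

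**Conclusion.** The point holds in limited form. The percentage rule in 8.1.3 is wrong as written for Enrolled Set demographics and for any percentage in the all-AE row of the overall AE table. It is right for Safety Set tables and for treatment-emergent rows.

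That demographic totals exceed 100% needs only one consented patient who is never dosed. The size, about 111% to 143% with about 24 dosed, restates the assumed 10% to 30% never-dosed share and is not an estimate from the documents. A reader might take the matching factors of 1.11 to 1.43 as a general inflation of AE rates; they are not.

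The consequence is minor. The primary objective is safety and tolerability, the Safety Set consists of dosed subjects by definition, and SAP 8.4.3 plans no formal hypothesis testing.

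**What to change.** Change the 8.1.3 sentence to: *Unless otherwise indicated, percentages are based on the number of subjects in the analysis set and column of the table.* Enrolled Set demographics and the all-AE row then use the Enrolled Set number.

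State two exceptions with it:
- Treatment-emergent AE rows keep dosed subjects as the denominator, including in Enrolled Set tables.
- Menopause status keeps female patients as the denominator, as SAP 12.2 already says.

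Also state that never-dosed patients are counted in the overall column of Enrolled Set tables. A separate column for them is optional. Check the Appendix 4 shells against the revised wording.

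The cost is a few sentences in the SAP and a check of the shells. No new data are needed.
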